8.4. Exploratory Efficacy Analyses

8.4.1. Acute-on-Chronic Liver Failure (ACLF)

Shift tables (i.e., status at baseline versus status at follow-up visit) will be presented for the Chronic Liver Failure Consortium Acute Decompensation score (CLIF-C ADs) using the categories: CLIF-C ADs ≤ 45 , $45 < \text{CLIF-C ADs} \leq 60$, and CLIF-C ADs > 60 . The number and percentage of subjects in each category will be presented by treatment group and visit.

8.4.2. Biochemical Responder Analyses

The percentage of subjects that meet the following criteria of a responder based on each of the definitions below will be summarized by treatment group and at each study visit:

- Decrease in ALP of $\geq 15\%$ and $\geq 40\%$ from Baseline
- ALP $\leq \text{ULN}$
- ALP $\leq 3x \text{ ULN}$ and AST $\leq 2x \text{ ULN}$ and total bilirubin $\leq \text{ULN}$ ([Corpechot 2008](#))
- ALP $\leq 1.5x \text{ ULN}$ and AST $\leq 1.5x \text{ ULN}$ and total bilirubin $\leq \text{ULN}$ ([Corpechot 2011](#))
- ALP $\leq 1.67x \text{ ULN}$ and total bilirubin $\leq \text{ULN}$ ([Momah 2012](#))

- Normal bilirubin (values \leq ULN) and normal albumin (values \geq lower limit of normal) (Kuiper 2009)
- ALP \leq 1.76x ULN (Kumagi 2010)

Responder analyses will compare treatment groups using a CMH test stratified by the randomization stratification factor. Missing values will be considered as a non-responder.

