3. SUMMARY OF STUDY DESIGN

[figure not shown]
This Phase 4, double-blind, randomized, placebo-control, multicenter study will evaluate the effect of OCA on clinical outcomes in subjects with PBC who are at higher risk of liver-related clinical complications.

Eligible subjects will have a diagnosis of PBC with bilirubin levels $>ULN$ and $\leq 5x ULN$ and/ or $ALP > 3x ULN$. Subjects will be screened twice during a 1- to 8-week Screening period prior to entering the study to allow for the collection of repeat serum chemistry samples (at least 2 weeks apart) to confirm pretreatment alkaline phosphatase (ALP) and total bilirubin values.

Investigational product (IP) will be taken orally, once daily for the majority of subjects; dose and frequency will be modified for subjects with cirrhosis (including subjects progressing to cirrhosis during the study) and classified as Child-Pugh B or C. The randomization will be stratified by ursodeoxycholic acid (UDCA) treatment (yes/ no) and baseline bilirubin categories ($>$ upper limit of normal [ULN]/ $\leq ULN$). A minimum of 30% of subjects will have elevated bilirubin ($>ULN$) at Screening.

The study is event driven and will continue until approximately 127 adjudicated primary endpoint events have been accrued in unique subjects, or until the Sponsor (eg, based on a recommendation from the Data Monitoring Committee (DMC)) terminates the study. Subjects are expected to be followed for a minimum of approximately 6 years. Figure 1 below displays the study design diagram. Schedules of study procedures are outlined in Table 1 (Screening to Month 12) and Table 2 (Year 2 to End-of-Study Endpoints) of the study protocol, where more details are provided.

Figure 1: Schematic Diagram Study 747-302

EOS = end of study; M = month, OCA = obeticholic acid; ULN = upper limit of normal
 Initial dose titration of investigational product should occur at the Month 3 visit, or any study visit thereafter for subjects on all dosing regimens, based on tolerability and biochemical response (Up-titration should be considered when ALP and/ or total bilirubin are $>ULN$). Subsequent dose titration(s) for subjects classified as Child Pugh B or Child-Pugh C and following a modified dosing schedule may occur no earlier than 6 weeks after the previous dose titration.

Dosing frequency will be determined by the presence or absence of cirrhosis and, if cirrhosis is present, by Child-Pugh Score as described below:

	Planned Dosing Regimen	

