4. ANALYSIS POPULATIONS AND APPROACHES TO ANALYSIS

4.1. Intent-to-Treat (ITT) Population

The ITT Population includes all randomized subjects who receive any amount of investigational product (OCA or placebo). The ITT Population will be the primary population used for efficacy analyses. Treatment assignment will be based on the randomized treatment.

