8.3.2. Liver Biochemistry Analyses

Analyses of changes in liver biochemistry (gamma-glutamyl transferase (GGT), ALT, AST, conjugated bilirubin, albumin, and INR) at each visit will be compared between treatment groups using a restricted maximum likelihood based mixed-effect model repeated measures (MMRM) with treatment, baseline, visit, visit by treatment interaction and randomization stratification factors to be included in the model. Visits through Month 24 will be included. An unstructured covariance model will be used. If the computational algorithm fails to converge, the following structures will be tested in the order: Toeplitz, AR(1) and compound symmetry (CS). If the model still does not converge, the stratification factors will be dropped from the model one at a time (UDCA followed by bilirubin).

Change from Baseline over time will be analyzed using analysis of covariance (ANCOVA) with change from Baseline as the dependent variable including treatment group and randomization stratification factor as fixed effects and the Baseline values as a covariate. Descriptive statistics of the laboratory values will be summarized by treatment group. The results, change from

Baseline, and percentage change from Baseline values, as well as estimates of least-square means, standard errors, and 95% CIs, will be presented by treatment group. Estimates of the mean difference between treatment groups, the standard error of the difference, and 95% CI of the difference will be presented.

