All statistical tests comparing groups will be conducted at the 2-sided, 0.05 level of significance, unless otherwise specified (eg, the primary efficacy analysis, [Section 8.6](#)). Summary statistics for each treatment group will be presented, as well as 95% CIs comparing groups.

Baseline Definitions

The Baseline value for statistical analyses of quantitative parameters is defined as the mean of all available study evaluations after the subject signs the informed consent and prior to or on the first administration of investigational product, unless otherwise specified. If there is only one evaluation prior to the first administration of investigational product then the available data from this evaluation will be used as the Baseline value.

The baseline value for analyses of lipid parameters is defined as the last fasted evaluation prior to the first administration of IP.

The baseline value for analyses of qualitative parameters (eg, normal/abnormal) is defined as the last evaluation prior to the first administration of IP.

Baseline values defined above will not change regardless if a subject stops taking investigational product and begins taking commercially marketed OCA.

Visit Windows

Visit windows, as provided below, will be established relative to an individual’s Day 0, the date of first administration of investigational product. Analyses will use visit windows defined by relative day, overriding CRF designated visit numbers.

OCA Therapy 3-Month Interval Visit Windows (Days)

Months	Target Study Day ^a	Analysis Window Study Day ^a	
		Low	High
Day 0	1	Closest visit to Day 1, prior to first IP dose ^b	
Month 1	30	2	46
Month 3	90	47	137
Month 6	183	137	227
Month 9	274	228	318
Month 12	365	319	410
...
Month n^b	$\text{round}(365.25/12*n)$	$\text{round}(365.25/12*n) - 46$	$\text{round}(365.25/12*(n+3)) - 47$

Note: Follow-up visits are not included in visits windows.

^a Study day will be calculated from first dose date.

^b For n in three month increments (15, 18, 21, ...).

Partial Dates

If only a partial date is available and is required for calculation, the following standards will be applied:

- Diagnostic Date (eg, PBC diagnostic date)
 - For missing day only – Day will be imputed as the first day of the month (ie, 1).
 - For missing day and month – Day and month will be imputed as the first day of the year (ie, 1 January).
- Start Dates (eg, event date, AE onset date, or start date of medication)

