Percentages based on frequency counts will be based on available data, and denominators will generally exclude missing values, unless otherwise stated. For frequency counts of categorical variables, categories whose counts are zero will be displayed for the sake of completeness. For example, if none of the subjects discontinued due to “lost to follow-up,” this reason will be included in the table with a count of 0. Percentages based on frequency counts will be presented as a whole number (no decimal places), and values less than 1% will be presented as “<1%.” Values less than 100% but that round up from 99.5% to 100% will be presented as “>99%.”

Quantitative laboratory tests containing less than (<) and greater than (>) symbols are test results that are below and above quantifiable limits, respectively. In order to retain these values for analysis purpose, the following imputations will be done within the analysis datasets:

For laboratory test results that are below the quantifiable limit:

Imputed laboratory results = (numeric portion of the result) x 0.9.

For laboratory test results that are above the quantifiable limit:

Imputed laboratory results = (numeric portion of the result) x 1.1.

For the purpose of tabulations, the unscheduled post-baseline values generally will be excluded from summary tables, but will be included in data listings. Unscheduled visits will be considered for analyses of shift from baseline to worst value (low-normal-high).

Standard Calculations

Variables requiring calculation will be derived using the following formulas:

- First dose date is defined as the day of first dose of IP received after randomization
- Last dose date is defined as day of the last dose of IP
- Time to event – The time to an event will be calculated in days as the date of the first occurrence of the event minus the date of first investigational product administration plus 1
- Days – A duration expressed in days between one date (*date1*) and another later date (*date2*) will be calculated using the following formulas:

duration in days = $date2 - date1 + 1$, where $date1 \geq$ first dose date

duration in days = $date2 - date1$, where $date1 <$ first dose date

- Months – A duration expressed in months is calculated as the number of days divided by 365.25/12 (approximately 30.4)
- Years – A duration expressed in years between one date (*date1*) and another date (*date2*) is calculated using the following formulas:

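### Section 8.4.2 counts visits that fell after study close-out as non-response, so late-visit biochemical response rates shrink for calendar reasons

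*SAP*

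**What the plan says.** Section 8.4.2 lists seven biochemical response criteria built from ALP, AST, total bilirubin and albumin. The percentage meeting each one "will be summarized by treatment group and at each study visit". On testing it says: "Responder analyses will compare treatment groups using a CMH test stratified by the randomization stratification factor". Its last sentence is the missing-data rule: "Missing values will be considered as a non-responder". The section names no analysis set, no last visit and no minimum number of subjects at a visit.

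Other parts of the SAP bear on this:

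- **Analysis set.** Section 4.1: "The ITT Population will be the primary population used for efficacy analyses". ITT therefore applies by default.
- **General denominator rule.** Appendix A (Data Conventions) says that "denominators will generally exclude missing values, unless otherwise stated". Section 8.4.2 does state otherwise.
- **Visit grid.** In Appendix A (Visit Windows) the footnote reads "For n in three month increments (15, 18, 21" and continues with an ellipsis, so the grid has no end.
- **Follow-up.** Section 3: "The study is event driven and will continue until approximately 127 adjudicated primary endpoint events". Follow-up length therefore varies between subjects. Section 14.1 records that the study was stopped early, at about 67% information (84 events).
- **Contrast.** The repeated-measures model in Section 8.3.2 has a cap: "Visits through Month 24 will be included". Section 8.4.2 has none.

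**The concern.** Non-responder imputation is a defensible choice for a visit that was due and missed. It has no such basis for a visit that could not have taken place because the study had closed. Section 8.4.2 does not separate the two.

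The planned design largely hid this. With 4 years of accrual and 6 years of follow-up (Section 3.2), every subject would have reached Year 6. Early stopping removes that protection, and the interim SAP (Section 6.4) reports slower enrolment than expected. The final SAP was revised for the early stop, but this rule carries no matching restriction.

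What is at stake is how the late rows of the table are read. A response rate that is truly constant would appear to decline with visit number in both arms, and the absolute difference between arms would shrink with it. Durability of response could not be judged from such a table. This has some weight here: the clinical pharmacology plan (Section 2) notes that accelerated approval rested on ALP reduction, and Section 8.7 of the SAP foresees further work on biochemical improvement if it correlates with outcomes.

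**Working it through.** **1. The plan's own figures.** The SAP gives no figure for the responder analysis. The only figures tied to the accrual pattern are 127 events and about 428 subjects (Section 3.2), and these reproduce closely.

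- Inputs: two-sided 5%, 80% power, HR 0.60, 1:1, placebo survival 0.6 at 8 years, 4 years' accrual, 10 years in total, 10% dropout.
- Events: Freedman's formula gives 126 and Schoenfeld's gives 121, against 127. By Schoenfeld's formula, power with 127 events is 0.82.
- Subjects: exponential survival with uniform 4-year accrual gives an average event probability of 0.331. Then 127/0.331 = 384, and 384/0.9 = 427, against 428.

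**2. Share of subjects for whom a visit was due.** For uniform accrual over A years and study length L years, the share due at year t is

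s(t) = min(1, (L − t)/A).

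The actual accrual curve and study length are not in the documents. The clinical pharmacology plan says only that the study began before approval on 27 May 2016, and Appendix A uses close-out dates in 2022. The 7.5-year stop and the 6-year accrual are therefore assumptions. The 4+6 and 10+2 patterns are the documents' own (SAP Section 3.2; interim SAP Section 5.2).

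| Scenario | Month 24 | Month 36 | Month 48 | Month 60 | Month 72 | Month 84 |
|---|---|---|---|---|---|---|
| A=4, L=10 (as planned) | 100% | 100% | 100% | 100% | 100% | 75% |
| A=4, L=7.5 (stop assumed) | 100% | 100% | 87.5% | 62.5% | 37.5% | 12.5% |
| A=6, L=7.5 (both assumed) | 92% | 75% | 58% | 42% | 25% | 8% |
| A=10, L=12 (interim SAP scenario) | 100% | 90% | 80% | 70% | 60% | 50% |

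Example: A=4, L=7.5, Month 60 gives (7.5 − 5)/4 = 0.625. With L=7.5, accrual over 5 or 7 years gives a Month 48 share of 3.5/5 = 70% or 3.5/7 = 50%. At Month 12 the share is 100% in all four tabulated scenarios.

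**3. Effect on the reported rates.** Under the rule as written, reported rate = true rate × s(t), before any dropout. Take an illustrative constant response of 40% on OCA and 15% on placebo (assumed; the documents give no rates). The true difference is 25 points throughout, and the reported difference is 25 × s(t):

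- A=4, L=7.5: 21.9 points at Month 48, 15.6 at Month 60, 9.4 at Month 72, 3.1 at Month 84.
- A=6, L=7.5: 14.6 points at Month 48 (about 23% vs 9%) and 6.25 at Month 72 (10% vs about 4%).

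The ratio of the two rates does not change, because s(t) multiplies both arms.

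**4. Effect on the test.** About 334 subjects were enrolled (clinical pharmacology plan, Section 5), or 167 per arm at 1:1. Power for two proportions is Φ((|p1 − p0| − 1.96·SE0)/SE1), with SE0 pooled and SE1 unpooled. The rule as written uses n = 167 per arm and rates p·s. The due-only analysis uses n = 167·s per arm and rates p. For A=4, L=7.5:

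| Visit | Rule as written | Due only |
|---|---|---|
| Month 60 | 0.97 | 0.99 |
| Month 72 | 0.81 | 0.89 |
| Month 84 | 0.35 | 0.44 |

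The loss of power is modest. Attenuation of the rates is the larger effect.

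**The case against.** **Missing values may mean values absent at a visit that was due.** Someone applying the rule sensibly might leave never-due visits out, and Appendix A generally excludes missing values from denominators. But that default yields wherever the plan states otherwise, as Section 8.4.2 does, and nothing in the SAP restricts the rule to visits that were due. The literal reading is the one a programmer would implement.

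**The analysis is exploratory.** This stands. Section 8.4.2 lies outside the testing hierarchy of Section 8.6, and no confirmatory claim rests on it. The outcome analysis tied to the post-marketing requirement (Section 8.4.3) uses the same missing-value rule but at the 12-month visit, where few subjects would be not yet due.

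**The arm comparison is biased.** A reader might infer this, but the documents do not support it. Study closure is unrelated to the randomised arm, so never-due visits should be balanced. Type I error is not inflated; the effect is attenuation and some lost power.

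**Response rates fall towards zero.** A reader might infer this too, but it depends on an accrual pattern that is not given. Under the planned 4-year accrual with an assumed 7.5-year stop, nobody is affected at Month 36 and 12.5% at Month 48. The 6-year case is less favourable and is also assumed.

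**Other tables show persistence.** Section 9.4.2 summarises ALP, AST, total bilirubin and albumin at each on-study visit without non-responder imputation. That limits the harm. However, those are descriptive safety summaries, which exclude data after commercial OCA starts (Section 9), and they do not report responder status.

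**Conclusion.** The point holds as a defect in an exploratory, late-visit analysis. Section 8.4.2 compares response at every visit of an open-ended grid and sets all missing values to non-response. It has no last visit and no exclusion of subjects whose visit fell after close-out. Late rates and absolute arm differences are understated by the share of subjects not yet due. Month 12 is unaffected in the tabulated scenarios, and Month 24 little or not at all.

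The size is uncertain because accrual and study length are not given. Across the early-stop and long-accrual scenarios above, between 30% and 58% of subjects would be wrongly counted as non-responders at Month 60. The 40% vs 15% response rates serve only as illustration.

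The documents do not support a claim of bias in favour of either arm, or of damage to the primary or key secondary conclusions. Nor is non-responder imputation itself at fault: it remains reasonable for visits that were due and missed.

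**What to change.** In Section 8.4.2, define the denominator at each visit as ITT subjects whose target study day for that visit fell on or before study close-out, plus any subject with an observed value in the visit window. Apply missing = non-responder only within that denominator. Report the number due and the number observed at each visit.

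Two details matter:

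- **Use the target day, not the end of the window.** The Month 12 window runs from Day 319 to Day 410. Requiring it to have closed would discard a real Day 365 result if close-out fell on Day 380.
- **Name the close-out date.** The multiple-imputation steps in Appendix A give 12 Feb 2022 as an example for the start of close-out but use 12 Aug 2022 in the derivations.

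Capping the tests at Month 24, as in Section 8.3.2, would not fully solve the problem: under 6-year accrual about 8% are still not due at that visit.

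The cost is a short addition to the text and one flag in the analysis dataset. The downside is smaller denominators and less precise estimates at late visits, although in the calculation above power is slightly higher than under the rule as written.

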8.4.3. Time-to-Event by Biochemical Response

Additional efficacy analyses of correlation of time-to-event outcomes and biochemical response will be run as supportive information for primary endpoint evaluation and in support of FDA PMR 3057-3 as described below.

A biochemical responder is defined as a subject who attains an ALP <1.67 times the upper limit of normal (ULN) and total bilirubin \leq ULN and an ALP decrease of $\geq 15\%$ from Baseline at their 12-month visit. Subjects missing values are considered non-responders. The number and percent of subjects censored and with events and descriptive statistics for the time-to-event will be presented by biochemical response. KM estimates of the distribution of the time-to-event using the primary composite endpoint will be tabulated and graphed by treatment group and biochemical responder status. KM tabulations will present time to event in days; KM graphs will present time to event in months.

Biochemical responders and non-responders will be compared using a log rank test stratified by treatment group. The proportionality of hazards will be assessed using Schoenfeld residuals and the hazard ratio and 95% CI will be estimated based on a Cox regression model stratified by treatment group.

The analysis will be repeated using the following alternative definitions of biochemical responder:

- ALP ≤ 2.0 x ULN at their 12-month visit
- Total bilirubin <1 x ULN at their 12-month visit

For placebo subjects, OCA-treated subjects, and all ITT subjects, additional KM estimates of the distribution of the time-to-event will be graphed by biochemical response for the combined ALP and bilirubin categories:

1. ALP ≤ 2.0 x ULN and Total bilirubin <1 x ULN at their 12-month visit
2. ALP >2.0 x ULN and Total bilirubin <1 x ULN at their 12-month visit
3. ALP ≤ 2.0 x ULN and Total bilirubin ≥ 1 x ULN at their 12-month visit
4. ALP >2.0 x ULN and Total bilirubin ≥ 1 x ULN at their 12-month visit

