	Standard	Modified
	Noncirrhotic/ Child-Pugh A	Child-Pugh B or Child-Pugh C
Starting Dose ^a (Day 0)	5 mg daily	5 mg once weekly
Titration 1 ^b (≥Month 3)	10 mg daily	5 mg twice weekly
Titration 2 ^b (≥6 weeks after Titration 1)	NA	10 mg twice weekly

^a Starting dose based on subject's cirrhosis status and Child-Pugh Score at Screening.

^b Planned titration regimen is shown; however, the titration of dose and/or frequency is dependent on subject tolerability, biochemical response, and/or changes in cirrhosis status or Child-Pugh Score at any time during the study

^c Dosing per the twice weekly schedule must be at least 3 days apart.

With the exception of liver transplant, if a subject experiences a suspected or confirmed clinical outcomes event, the subject should continue the regular visit schedule and continue taking IP as long as the subject has not met any of the criteria for discontinuation outlined in the protocol. Subjects who discontinue IP are expected to be followed through to study closure (or at the discretion of the Sponsor).

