- Age categories (at time of informed consent): <65 years, ≥ 65 years
- Age categories at PBC Diagnosis (at time of informed consent): <50 years, ≥ 50 years
- Race: white, non-white
- Ethnicity: Hispanic, non-Hispanic
- Baseline bilirubin level: $>ULN$, $\leq ULN$
- Baseline use of UDCA: Yes, No

The primary efficacy endpoint will also be assessed across the spectrum of PBC disease stage as defined by Rotterdam criteria ([Kuiper 2009](#))

- Early (normal albumin and normal bilirubin)
- Moderate (abnormal albumin or abnormal bilirubin)
- Advanced (abnormal albumin and abnormal bilirubin)

If a strong correlation between biochemistry and clinical outcomes using the ITT population is observed, the biochemical improvement in the subpopulations (baseline disease stage, Rotterdam disease severity, and monotherapy) will be further assessed.

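### SAP 8.4.3 relates Month-12 biochemical response to events counted from first dose with no landmark, which tilts the comparison towards responders by an amount the documents do not fix

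*SAP*

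**What the plan says.** Section 8.4.3 defines a responder by ALP below 1.67 times ULN, total bilirubin no higher than ULN, and "an ALP decrease of $\geq 15\%$ from Baseline at their 12-month visit". Two alternative definitions, one on ALP alone and one on bilirubin alone, are also read at 12 months. For missing data the rule is "Subjects missing values are considered non-responders". The test is fixed: "Biochemical responders and non-responders will be compared using a log rank test stratified by treatment group". A Cox model with the same stratification and Kaplan-Meier curves accompany it.

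Appendix A, Standard Calculations, sets time to event as "the date of the first occurrence of the event minus the date of first investigational product administration plus 1". The estimand table in 8.1 counts from randomization instead; either origin precedes Month 12. The Month 12 window in Appendix A runs from Day 319 to Day 410. Neither 8.4.3, Appendix A nor the matching section 4.3.2 of the interim SAP has a landmark, an exclusion of earlier events, or a time-dependent responder status.

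On purpose, 8.4.3 says the analyses "will be run as supportive information for primary endpoint evaluation and in support of FDA PMR 3057-3". Section 8.7 makes further subpopulation work conditional: "If a strong correlation between biochemistry and clinical outcomes using the ITT population is observed".

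**The concern.** Being a responder requires a sample in the Month 12 window, so a responder's time from first dose up to that sample is guaranteed free of death and of any event that stops sampling. Non-responders have no such guarantee, and the missing-value rule adds every such early event to their count.

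A second route works even when the sample exists. The primary composite counts new total bilirubin above 3 mg/dL, and MELD-based events whose formula includes bilirubin. The main responder definition requires bilirubin no higher than ULN. A bilirubin event at Month 6 can thus itself produce non-response at Month 12, so the outcome comes first and sets the group it is tested against.

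Whether biochemical response tracks clinical outcome is the question this analysis is meant to inform, and both routes push the answer towards yes.

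**Working it through.** **Inputs from the SAP (3.2).** Placebo event-free 0.6 at 8 years, hazard ratio 0.60, 1:1 allocation, 4 years of accrual plus 6 of follow-up, 10% dropout, 127 events, 428 subjects. The clinical pharmacology plan, section 5, gives about 334 enrolled.

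**The plan's own figures first.** Freedman: (1.960 + 0.842)² × (1.6/0.4)² = 7.85 × 16 = 126 events, against 127 stated. Hazards: −ln(0.6)/8 = 0.0639 per year on placebo, × 0.60 = 0.0383 on OCA. With uniform accrual the mean event probability is 0.331, so 127/0.331 = 384 and 384/0.9 = 427, against 428. The inputs reproduce the design.

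**Year-1 events.** Placebo 1 − exp(−0.0639) = 6.2%; OCA 1 − exp(−0.0383) = 3.8%. In 334 subjects: 167 × (0.062 + 0.038) = about 17.

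**Null simulation.** 2,000 trials per setting, SAP hazards, true responder hazard ratio 1, log rank and Cox stratified by treatment, missing counted as non-response. Not in the documents, so assumed and varied: f, the share of year-1 events that leave no Month-12 value; responder rates from 5%/20% to 30%/50% (placebo/OCA); dropout of 2% per year.

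| f | Responder HR, clock from first dose | Two-sided 5% rejection |
|---|---|---|
| 0 | 0.99-1.01 | about nominal |
| 0.25 | 0.94-0.96 | 4%-7% |
| 0.5 | 0.88-0.92 | 5%-11% |
| 1 | 0.77-0.83 | 6%-27% |

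A separate run with 6 to 10 years of follow-up gave 0.99, 0.95, 0.91 and 0.79 at the same four values of f.

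**Hand check.** With 334 subjects, 16.5 of 102.7 simulated events fall in year 1, a share s = 0.161. Moving a fraction f of these from responders to non-responders gives HR ≈ (1 − f·s) / (1 + f·s·r/(1 − r)), where r is the responder rate. For f = 1: r = 0.10 gives 0.839/1.018 = 0.82, and r = 0.40 gives 0.839/1.107 = 0.76. The simulated value for 10%/40% is 0.79, between the two. For f = 0.5 the formula gives 0.91 and 0.87 (simulated 0.89).

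**Higher event rate or shorter follow-up.** With the event rate doubled (assumed, for the expanded endpoint) and/or dropout of 10%-20% per year, responders 10%/40%: 0.93-0.95 at f = 0.25, 0.84-0.89 at f = 0.5, and 0.66-0.77 at f = 1 (rejection 13%-26%).

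**With a Month-12 landmark.** Median HR 0.98-1.02 and rejection 4.4%-6.0% in every setting.

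The simulation sets response independent of hazard, so it does not include the bilirubin overlap.

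**The case against.** The strongest objection is that most early events should not remove the Month-12 sample. Section 3 says that after an outcome event other than transplant "the subject should continue the regular visit schedule and continue taking IP", provided no discontinuation criterion is met, and most components of the composite are non-fatal. At f = 0 the missing-value route gives no bias, and at f = 0.25 rejection stays close to nominal. This stands: f should be below 1. It does not remove the problem, because deaths always count, and subjects who keep attending are those in whom an early bilirubin event can decide the classification.

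A reader might infer a much larger artefact, with a responder hazard ratio of 0.60-0.66 and rejection up to 59%. Such figures need every early event to end in non-response, together with short follow-up or hazards up to 0.20 per year, about three times the SAP's 0.064. The documents do not support that combination.

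A reader might also infer that early dropout itself favours responders. It does not: early leavers without events add event-free time to non-responders. With f = 0 and uniform censoring from day 0, the hazard ratio was 1.01-1.14.

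Nor is the missing-value route shown for the four combined ALP/bilirubin curves. Section 8.4.3 does not say where subjects with missing values go in those figures, and it attaches no test to them. If only observed values are classed, all four groups share the same survival requirement.

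Finally, section 8.4 is exploratory and outside the testing hierarchy in 8.6. Section 8.7 sets no threshold for its correlation and does not cite 8.4.3. This also stands and limits the consequence.

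**Conclusion.** The point holds in a limited form. As fixed in the SAP, the classification time, missing-value rule, time origin and test together bias the comparison towards a responder benefit. On the SAP's hazards and the assumed responder rates, the artefact runs from none to a hazard ratio of 0.77-0.83, depending on f, and can be larger with more events or shorter follow-up. The trial stopped early and the endpoint was expanded (14.1), so either is possible. The effect of the bilirubin overlap is not quantified. It applies directly to the two definitions that use bilirubin, not to the ALP-only one.

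The primary and key secondary tests are unaffected. The change is still worth making, because the SAP assigns this analysis a supportive role for the primary endpoint and a regulatory requirement.

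**What to change.** Make the log rank, Cox and Kaplan-Meier comparisons in 8.4.3 a landmark analysis for all three responder definitions:

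- include ITT subjects who are event-free and still followed at the close of the Month 12 window (Day 410);
- classify on values up to then and measure time from Day 410;
- show subjects with no Month-12 value as a separate group, with a sensitivity analysis counting them as non-responders.

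Use the same landmark for the four ALP/bilirubin figures, so that their curves contain no guaranteed event-free time, and state how missing values are handled there.

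The cost is SAP wording and the early events in this exploratory analysis. At the SAP hazards that is about 17 events in 334 subjects over the first year. Up to Day 410 (410/365.25 = 1.12 years) it is 167 × (0.069 + 0.042) = about 19. The expanded endpoint may lose more. No new data are needed.
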